## **1.0 INTRODUCTION**

### **1.1 Name of Study Disease/Stage: Breast cancer with brain metastases**

### **1.2 Name of Investigational Agent: Eribulin Mesylate**

#### **1.3 Clinical Data for Eribulin:**

Eribulin mesylate (Halaven®) is a microtubule inhibitor approved by FDA in metastatic breast cancer patients who have received at least two prior chemotherapy regimens for metastatic disease. Multiple phase 2 studies and one noteworthy phase 3 study have established the efficacy of eribulin mesylate (Halaven®) in patients with metastatic breast cancer (MBC) (1-4). The efficacy of eribulin mesylate has also been evaluated in other advanced solid tumors. These phase 2 studies have demonstrated that eribulin mesylate shows activity in patients with advanced non small cell lung cancer, prostate cancer, soft tissue sarcoma and platinum-susceptible ovarian, fallopian tube or peritoneal cancers. Eribulin mesylate was evaluated in a Phase 3, open label, randomized trial for patients with metastatic or locally recurrent breast cancer against the therapy of physician's choice (TPC) (4). Eribulin mesylate 1.4mg/m^2 was administered intravenously over 2-5 minutes on days 1 and 8 of 21 days cycles; the median duration of treatment was 3.9 months. TPC included chemotherapy (96% received single agent vinorelbine, gemcitabine, capecitabine, taxanes, or anthracyclines) or hormonal therapy. The median duration of treatment in the TPC arm was 2.1 months for chemotherapy and 1 month for hormonal therapy. Participants had either received, responded poorly or became refractory to at least 2 prior chemotherapy treatments including an anthracycline and taxane unless contraindicated either the adjuvant or metastatic setting. Overall, 16% of the patients had human epidermal growth factor receptor 2 (HER2)-positive disease and 19% were estrogen receptor (ER), progesterone receptor (PR) and HER2- negative (triple-negative). Although only 2 previous chemotherapy regimens were mandatory for enrollment, 9% of patients had received 4 or more chemotherapy regimens. For the 508 women treated with eribulin mesylate, the median overall survival (OS) was 13.1 months; the median OS was 10.6 months in 254 women in the TPC arm ( $p = 0.041$ ). A significantly higher overall response rate (ORR) was also found with eribulin mesylate compared to TPC (12% vs. 5%) ( $p = 0.002$ ). Further analysis of the study results suggested that survival benefit with eribulin mesylate was independent of age without resulting in additional toxicity in older patients. Hence, it was recommended that age alone should not preclude older patients from receiving the drug regimen (5). Overall, this study demonstrated that eribulin mesylate was an effective agent associated with survival benefit compared to other standard regimens in heavily pretreated patients with locally advanced breast cancer or MBC. This trial formed the basis for the 2010 United States Food and Drug Administration approval of eribulin mesylate for advanced breast cancer after two or more chemotherapy regimens.

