## **3.0 STUDY DESIGN**

### **3.1 Design:**

This is a phase II study that will require 20 patients to evaluate the primary objective (CNS PFS at 3 months). Study patients will have a baseline brain MRI and a second MRI at 12 weeks to evaluate disease.

**3.2 Number of Subjects:** A total of 20 evaluable patients will be required for the study:

**3.3 Expected Duration of Subject Participation:** Death or disease progression or toxicity.

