### **3.4. Duration of Therapy**

In the absence of treatment delays due to adverse events, treatment may continue on study until one of the following criteria applies:

- Systemic or CNS disease progression,
- Intercurrent illness that prevents further administration of treatment,
- The investigator considers it, for safety reasons, to be in the best interest of the patient.
- Unacceptable treatment related toxicity, NCI CTC AE version 4.0. Grade 3 or 4 that fails to recover to baseline or < Grade 2 in the absence of treatment within 4 weeks
- General or specific changes in the patient's condition render the patient unacceptable for further treatment in the judgment of the investigator,
- Patient decision to withdraw from treatment (partial consent) or from the study (full consent),
- Pregnancy during the course of the study
- Death

The date and reason for discontinuation must be documented. Every effort should be made to complete the appropriate assessments.

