### **3.6 Replacement of Subjects**

Subjects who do not obtain the two MRI scans (baseline and 12 weeks) will be considered not evaluable for response and will be replaced.

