## 10.2 Calendar

Study Days	Pre-Study	Cycles 1-4 Day 1	Cycles 1-4 Day 8	Cycles 4+ Days 1 and 8	30 Day Follow Up	Long term Follow-Up
REQUIRED ASSESSMENTS						
Informed Consent	X					
Demographics	X					
Medical History	X					
Height	X					
Weight	X	X		X c	X	X
Vitals (blood pressure, pulse, temperature, and respiratory rate)	X	X	X	X	X	X
Physical Examination	X	X		X c	X	X
Concomitant Medication Assessment	X	X	X	X c	X	X
Karnofksy PS	X	X	X	X	X	X
Baseline Symptoms	X	X f				
Adverse Event Assessment		X	X	X	X	X
CBC / diff / platelets/ b	X	X b	X b	X b	X	X
Serum Chemistry a,b	X	X b	X b	X b	X	X
PT/INR	X					
β-HCG, women of childbearing potential	X					
EKG	X					
DISEASE ASSESSMENT						
MRI brain with and without contrast	X			X d		
CT chest, abdomen and pelvis with IV contrast or total body FDG PET	X			X e		
TREATMENT						
Eribulin mesylate		X	X	X		

**a:** Albumin, alkaline phosphatase, total bilirubin, bicarbonate, BUN, calcium, chloride, creatinine, glucose, potassium, total protein, SGOT [AST], SGPT [ALT], sodium, Mg. Calculated creatinine clearance will be done if creatinine and/or BUN are abnormal.

**b:** Laboratory Studies: to be completed 0-3 days prior to eribulin administration

**c:** Day 1 only

**d:** MRI brain to be completed every 12 weeks while on study eribulin mesylate

**e:** CT chest/abd/pelvis or total body PET every 12 weeks in patients with systemic disease while on study eribulin mesylate.

**f:** cycle 1 day 1 only

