### **11.1 Antitumor Effect – CNS Metastases**

Patients will have a baseline MRI brain scan (within 30 days before initiation of therapy) and should be re-evaluated for response by MRI scan after 12 weeks of starting the study.

Response and progression by MR will be evaluated in this study using WHO/modified McDonald's criteria.

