#### 11.1.4 Response Criteria

##### Measurement of Response

Gadolinium-enhanced brain MRI will be checked at baseline, 12 weeks after starting treatment, and every 12 weeks thereafter until progression. The slice thickness of MRI should be less than 5 mm throughout the brain (2 to 3 mm thickness is highly recommended). MR imaging will be collected electronically for ad hoc central review of responses.

Response in the brain also will be measured using dimensional measurements (WHO/modified McDonald's criteria). Systemic responses will be assessed using the revised Response Evaluation Criteria in Solid Tumors (RECIST) guideline (version 1.1) (Eisenhauer 2009).

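### The calendar ties brain MRI to being on eribulin, while three sections require a week-12 MRI regardless; patients who stop early without CNS progression have no scheduled endpoint scan and are then replaced

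*Combined protocol and SAP*

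**What the plan says.** The documents give two schedules for the brain MRI.

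- **Tied to treatment.** Section 10.2, footnote d: "MRI brain to be completed every 12 weeks while on study eribulin mesylate". The MRI row is blank for the 30-day and long-term follow-up columns, and the matching assessment lists in section 10.1.1 name no MRI. Section 3.5 follows patients off drug for toxicity and survival only.
- **Not tied to treatment.** Section 3.1: "Study patients will have a baseline brain MRI and a second MRI at 12 weeks to evaluate disease". Section 11.1 says that patients "should be re-evaluated for response by MRI scan after 12 weeks of starting the study". Section 11.1.4 (Measurement of Response): "Gadolinium-enhanced brain MRI will be checked at baseline, 12 weeks after starting treatment, and every 12 weeks thereafter until progression".

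Eribulin can end before week 12 without any CNS event. Section 3.4 lists "Systemic or CNS disease progression" as a reason to stop, so systemic progression alone is enough. It also lists toxicity, intercurrent illness, investigator judgment and patient decision.

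Under section 3.6, subjects without both the baseline and the 12-week scan "will be considered not evaluable for response and will be replaced". The Evaluability paragraph of section 13.0 applies the same two-scan condition to the primary and secondary objectives.

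**The concern.** The week-12 MRI is the one scheduled scan that decides the primary endpoint. A site that books visits from the calendar has no instruction to obtain it once eribulin has stopped. The replacement rule then turns the missing scan into an exclusion, and the exclusion depends on something that happens after baseline and may be linked to prognosis.

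The 20 analysed patients would then lean towards those who stayed on drug for 12 weeks. If patients who stop early have a lower CNS progression-free rate, the reported proportion is too high and the rule of 8 or more out of 20 is easier to pass than planned. Later CNS PFS times and the duration of CNS response would also lose imaging at the point where treatment stops.

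**Working it through.** **Inputs from the plan (section 13.0, Sample size and study duration).** Uninteresting rate 15%; hoped-for rate 35%; 20 evaluable patients; positive if 8 or more are progression-free at 3 months; stated 95% CI for 8/20 of 18.5–61.5%.

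**Reproducing the plan's figure.** Wald interval: 0.40 ± 1.96 × √(0.40 × 0.60 / 20) = 0.40 ± 0.215, or 18.5% to 61.5%, as stated. The exact probability of 8 or more of 20 at a true 15% is 0.0059, about 0.6%.

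**Effect of excluding patients without the scan.** Let d be the share of treated patients who lack the week-12 MRI, and q their true 3-month CNS progression-free rate. If the rate among all treated patients is 15%, the rate among those retained is

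(0.15 − d × q) / (1 − d).

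Neither d nor q is in the documents; both are assumptions here.

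Worst case, q = 0 (every patient without the scan would have been a failure):

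| d | Treated to obtain 20 evaluable, 20/(1 − d) | Rate among retained | P(≥ 8 of 20) |
|---|---|---|---|
| 0% | 20 | 15.0% | 0.6% |
| 10% | 22.2 | 16.7% | 1.1% |
| 20% | 25.0 | 18.8% | 2.2% |
| 30% | 28.6 | 21.4% | 4.7% |

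Varying q at d = 20%:

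| q | Rate among retained | P(≥ 8 of 20) |
|---|---|---|
| 0% | 0.15/0.80 = 18.8% | 2.2% |
| 7.5% | (0.15 − 0.015)/0.80 = 16.9% | 1.2% |
| 15% | (0.15 − 0.03)/0.80 = 15.0% | 0.6% |
| 30% | (0.15 − 0.06)/0.80 = 11.3% | 0.1% |

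The direction of the bias therefore depends on q. It is upward only when q is below the overall rate, zero when they are equal, and downward when q is higher.

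**What keeping everyone in the denominator does to a borderline result.** With 8 successes, the Wald lower limit is 16.3% for 8/22 and 15.3% for 8/23, both above 15%. It is 14.5% for 8/24, which is not. On the exact interval the change comes one patient later: 15.6% for 8/24 and 14.9% for 8/25. Four or five replaced patients are enough to change the conclusion at the threshold.

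**The case against.** **The scan is required elsewhere.** A reader might infer that patients who stop early can never have the endpoint MRI. The documents do not support that. Sections 3.1, 11.1 and 11.1.4 ask for the scan with no on-treatment condition, and section 3.4 asks for every effort to complete appropriate assessments at discontinuation. What stands is narrower: the calendar does not schedule the scan, so whether it is done depends on which section a site follows. The effort clause names neither brain MRI nor week 12.

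**Systemic progression is a smaller route than it looks.** Systemic imaging is also every 12 weeks (section 10.2, footnote e), with the same ±7-day window (section 10.1.1). Scheduled detection of systemic progression thus falls at about the time of the brain MRI. Only progression found clinically or on an unscheduled scan takes a patient off drug earlier. This reduces the number affected, but leaves toxicity, intercurrent illness and patient decision.

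**After week 12 the conflict is less clear.** Section 11.1.4 continues scans "12 weeks after starting treatment, and every 12 weeks thereafter until progression" without saying which kind of progression. The Time to CNS Progression text counts brain or systemic progression. Section 3.3 ends participation at death, disease progression or toxicity. On that reading, scans after week 12 also end at systemic progression. This stands, and it is a reason to define the term.

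**CNS progression can be recorded without MRI.** The criteria table in 11.1.4.1 includes neurologic worsening and tumor-related steroid increase. True, but section 3.6 and Evaluability still require the scan for inclusion.

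**Two further inferences should not be drawn.** One is that the plan censors CNS PFS when treatment stops: section 13.1 gives no censoring rule either way. The other is that about 39% of patients would be affected. Section 1.3 reports that "the median duration of treatment was 3.9 months"; under exponential stopping, with 12 weeks = 2.76 months, 1 − 0.5^(2.76/3.9) = 0.39, and the worst-case P(≥ 8 of 20) would be about 9%. That median belongs to an earlier phase 3 trial in a different population. It covers stops for any reason, which would include CNS progression, so it does not estimate the share lost through footnote d.

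**Conclusion.** The conflict is real and touches the primary endpoint. Footnote d and the follow-up schedule leave out a scan that three sections require, and the replacement rule turns its absence into exclusion. It is clearest for patients who stop before week 12 for toxicity or another reason other than progression.

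The text establishes the conflict; it does not establish that the result will be inflated. That needs the excluded patients to have a lower CNS progression-free rate than the rest, which is plausible but not shown. For an assumed 10–30% without the scan, the false-positive probability at a true 15% lies between 0.6% (same rate as the others) and 1.1–4.7% (all failures). It should be corrected, and wording is enough to do it.

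**What to change.** 1. **Schedule.** Reconcile footnote d, the Cycles 4+ list and both follow-up schedules with sections 3.1, 11.1 and 11.1.4. The week-12 brain MRI should be scheduled for every treated patient who is alive and without documented CNS progression, whether or not eribulin has stopped.
2. **Definition.** State in 11.1.4 that, for brain MRI, progression means CNS progression, and continue the 12-weekly scans on that basis.
3. **Analysis set.** In section 3.6 and Evaluability, do not replace or exclude a patient for stopping treatment before week 12. Count documented CNS progression (including by the clinical criteria in 11.1.4.1) or death before week 12 as an event. State in advance how a patient counts who is alive with no recorded event and no scan.
4. **Censoring.** State in section 13.1 that CNS PFS is not censored merely because eribulin stopped.

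All four changes are needed: aligning the calendar alone would still leave patients who die or are too ill for the scan to be replaced.

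Cost: wording, and a few off-treatment scans. The week-12 scan is already required by three sections. Scans after systemic progression may be additional to what is now intended, and the sponsor should accept that knowingly. No dose or treatment rule is affected.

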## **11.0 MEASUREMENT OF EFFECT**

CNS and non-CNS disease will be followed during the course of the trial. The primary endpoint will be response in brain.

### **11.1 Antitumor Effect – CNS Metastases**

Patients will have a baseline MRI brain scan (within 30 days before initiation of therapy) and should be re-evaluated for response by MRI scan after 12 weeks of starting the study.

Response and progression by MR will be evaluated in this study using WHO/modified McDonald's criteria.

#### **11.1.1 Definitions**

Evaluable for toxicity All patients will be evaluable for toxicity from the time of registration to protocol.

Evaluable for objective response Only those patients who have measurable disease present at baseline, have received eribulin as per the protocol, and have had their disease re-evaluated will be considered evaluable for response. These patients will have their response classified according to the definitions stated below. (Note: Patients who exhibit objective disease progression prior to the end of cycle 1 will also be considered evaluable.)

Evaluable Non-Target Disease Response Patients who have lesions present at baseline that are evaluable, but do not meet the definitions of measurable disease, have received at least one cycle of therapy, and have had their disease re-evaluated will be considered evaluable for non-target disease. The response assessment is based on the presence, absence, or unequivocal progression of the lesions.

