### 5.0 **REGISTRATION**

All subjects who have been consented are to be registered in the OnCore Database. All subjects will be registered through Seidman Cancer Center CTU and will be assigned a study number by the study coordinator at [contact].

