### **8.3 Reporting Procedures for All Adverse Events (AEs)**

All participating investigators will assess the occurrence of AEs throughout the subject's participation in the study. Subjects will be followed for toxicity for 30 days after treatment has been discontinued or until death, whichever occurs first. The clinical course of each event will be followed until resolution, stabilization, or until it has been determined that the study treatment or participation is not the cause.

The investigator is responsible for ensuring that all adverse events observed by the investigator or reported by the subject which occur after the subject has signed the informed consent are fully recorded in the subject's case report form, subject's medical records, and/or any other institutional requirement. Source documentation must be available to support all adverse events.

A laboratory test abnormality considered clinically relevant (e.g., causing the subject to withdraw from the study), requiring treatment or causing apparent clinical manifestations, or judged relevant by the investigator, should be reported as an adverse event.

The investigator will provide the following for all adverse events:

- Description of the event
- Date of onset and resolution
- Grade of toxicity
- Attribution of relatedness to the investigational agent
- Action taken as a result of the event
- Outcome of event

In this study, descriptions and grading scales found in the NCI Common Terminology Criteria for Adverse Events (CTCAE) version 4.0 available at <http://ctep.cancer.gov> will be utilized for AE reporting.

Investigative sites will report adverse events to their respective IRB according to the local IRB's policies and procedures in reporting adverse events.

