#### **8.5 Reporting Procedures for Serious Adverse Events**

For the purposes of safety reporting, all adverse events will be reported that occur from day of registration through 30 days after the final dose of study drug. Adverse events, both serious and non-serious, and deaths that occur during this period will be recorded in the source documents. All SAEs should be monitored until they are resolved or are clearly determined to be due to a subject's stable or chronic condition or intercurrent illness(es). Related AEs will be followed until resolution to baseline or grade 1 or stabilization.

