### **Long term follow-up (Every 3 months)**

- Physical Examination
- Weight
- Vital signs including: blood pressure, pulse, temperature, and respiratory rate
- Concomitant Medications Assessment including prescription medications, OTC, and nutritional/herbal supplements.
- Adverse events assessment
- Complete Blood Count (CBC) with differential and platelets. ALC will be calculated from CBC and differential
- Serum Chemistries: albumin, alkaline phosphatase, total bilirubin, bicarbonate, BUN, calcium, chloride, creatinine, glucose, potassium, total protein, SGOT [AST], SGPT [ALT], sodium, Mg

- Calculated creatinine clearance will be done if creatinine and/or BUN are abnormal.
- Karnofksy Performance status

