### **11.2.1 Definitions**

Evaluable for toxicity: All subjects will be evaluable for toxicity from the time of their first treatment with eribulin.

Evaluable for objective response: Only those subjects who have measurable disease present at baseline, have received at least one cycle of therapy, and have had their disease re-evaluated will be considered evaluable for response. These subjects will have their response classified according to the definitions stated below.

**Note:** Subjects who exhibit objective disease progression prior to the end of cycle 1 will also be considered evaluable.

Evaluable Non-Target Disease Response: Subjects who have lesions present at baseline that are evaluable, but do not meet the definitions of measurable disease, have received at least one cycle of therapy, and have had their disease re-evaluated will be considered evaluable for non-target disease. The response assessment is based on the presence, absence, or unequivocal progression of the lesions.

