#### **Secondary Objective 2.2.2:** Toxicity

We will evaluate rates (and 95% CI) of toxicity in patients treated with eribulin.

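### The toxicity analysis for objective 2.2.2 has conflicting start points and evaluability rules and no stated analysis window

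*Combined protocol and SAP*

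**What the plan says.** **Who counts, and from when.**
- Section 11.1.1 (CNS metastases): "All patients will be evaluable for toxicity from the time of registration to protocol".
- Section 11.2.1 (non-CNS metastases), under the same label: "All subjects will be evaluable for toxicity from the time of their first treatment with eribulin".
- Section 13.1, the only analysis text for objective 2.2.2: "We will evaluate rates (and 95% CI) of toxicity in patients treated with eribulin".
- Section 13.0, Evaluability: a baseline and a week 12 MRI are required for inclusion in the primary and secondary objectives. Toxicity is a secondary objective (2.2.2) and is not exempted.

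**Recording and reporting.** Section 8.3 covers events "which occur after the subject has signed the informed consent are fully recorded in the subject's case report form". Section 8.5 says "all adverse events will be reported that occur from day of registration through 30 days after the final dose of study drug".

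**End of the period.** Sections 3.5 and 8.3 follow patients for toxicity until 30 days after discontinuation or death, whichever is earlier. Section 8.5 also ends at 30 days. Section 3.5 describes the later 3-monthly follow-up, which runs until death, as being for survival. The long-term list in section 10.1.1 nevertheless includes "Adverse events assessment", and the calendar in section 10.2 marks it in the long-term column.

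**The concern.** Toxicity belongs to the patient, not to the CNS or the systemic compartment, so one term should not have two start points. A treated patient's event between registration and first dose counts under 11.1.1 and not under 11.2.1.

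At the other end, section 3.4 stops eribulin at systemic or CNS progression, so patients in long-term follow-up may well be on other treatment. Adverse events are assessed at those visits, and no sentence keeps them out of the 2.2.2 rate. Section 13.1 also does not say whether the rate is all-cause or treatment-related.

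The MRI condition acts on the denominator. Patients who stop or die before week 12 may include those stopped for toxicity, which section 3.4 lists as a reason for discontinuation. A rate without them would probably be too low. Two analysts following different sections could report different rates and intervals from the same data.

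**Working it through.** The plan states no toxicity rate, interval or threshold, so there is no figure of its own to reproduce. The check is textual, followed by the arithmetic of what each reading does.

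**1. Sections side by side**

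| Question | One reading | Another reading |
|---|---|---|
| Start of evaluability | Registration (11.1.1) | First eribulin dose (11.2.1) |
| Patients analysed | Treated with eribulin (13.1) | Those with baseline and week 12 MRI (13.0, Evaluability) |
| End of toxicity period | 30 days, or death if earlier (3.5, 8.3; 8.5 also 30 days) | Assessment continues at 3-monthly visits (10.1.1, 10.2) |
| Window for the rate | None stated (13.1) | – |

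**2. Patients counted only for a pre-dose or later-therapy event**

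The rate is x/n. With n = 20 treated, one extra patient adds 1/20 = 5 points. For scale, section 8.1.2 gives grade 3 and grade 4 neutropenia as 28% + 29% = 57%, about 11 of 20. Section 8.1.3 gives grade 3 and 4 neuropathy as 8% + 0.4% = 8.4%, about 2 of 20. The number of extra patients is assumed to be 0 to 3. Intervals are exact (Clopper-Pearson) 95%.

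| Extra patients | Base 11/20 | Base 2/20 |
|---|---|---|
| 0 | 55% (31.5–76.9) | 10% (1.2–31.7) |
| 1 | 60% (36.1–80.9) | 15% (3.2–37.9) |
| 2 | 65% (40.8–84.6) | 20% (5.7–43.7) |
| 3 | 70% (45.7–88.1) | 25% (8.7–49.1) |

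**3. The MRI condition**

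Section 3.6 replaces patients without both scans, so 20 evaluable patients can mean more than 20 treated. Suppose a share d of treated patients lacks the week 12 scan. Then N = 20/(1 − d), rounded up, and N − 20 are left out. If 2/20 = 10% is reported, the rate among all treated lies between 2/N (none of those left out had the event) and (2 + N − 20)/N (all of them did).

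- d = 10%: N = 23, 3 left out; 2/23 = 8.7% to 5/23 = 21.7%.
- d = 40%: N = 34, 14 left out; 2/34 = 5.9% to 16/34 = 47.1%.

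The values of d are assumptions. The upper ends are bounds, not forecasts.

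**The case against.** Several stronger readings are tempting, and the documents do not support them.

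- **Never-dosed patients in the denominator.** A reader might infer this because section 5.0 says "All subjects who have been consented are to be registered in the OnCore Database" and 11.1.1 starts at registration. But 13.1 limits the rate to treated patients, and nothing says 11.1.1 overrides it. What remains is the timing of events in treated patients.
- **Consent and registration as rival analysis sets.** Sections 8.3 and 8.5 govern recording and reporting. Collecting more widely than one analyses is sound practice, provided the analysis window is stated. Here it is not.
- **Two conflicting end rules inside 3.5 or 8.3.** Thirty days or death, whichever is earlier, is a single rule. The tension is only with the long-term visits.
- **Brain-metastasis symptoms before eribulin routinely counted as toxicity.** The calendar leaves adverse-event assessment blank at Pre-Study and has a separate baseline-symptoms row. That limits the risk but does not remove it, since 8.3 records events from consent and 11.1.1 counts from registration.

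The best defence of the long-term assessments is that sections 3.5, 8.0 and 8.3 follow each event to resolution, stabilization or a finding that the study is not its cause. Section 3.5 also requires late, possibly related serious events to be recorded. The 3-monthly visits can serve those duties, and 8.3 records attribution for every event, so later-therapy events could be separated. This stands as a reason to keep following ongoing events. It does not settle the rate, because 13.1 states neither a cut-off nor a use of attribution.

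**Conclusion.** The point holds as a conflict in wording that leaves a pre-specified secondary objective without a single way to be computed. Three things need settling: the start (11.1.1 against 11.2.1), the MRI condition (13.0 against 11.1.1, 11.2.1 and 13.1), and the missing window in 13.1 while assessments continue beyond 30 days.

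The size is 5 percentage points for each patient, among 20 treated, counted only for a pre-dose or later-therapy event. The documents give no number of such patients. The MRI condition could move the rate further and probably downward, but that depends on an unstated number of missing scans and on the toxicity of those patients.

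The primary endpoint is not affected. It would go too far to conclude that the planned rate includes untreated patients, or that the long-term assessments should be deleted.

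**What to change.** In 13.1 and 11.1.1, state once:

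- **Analysis set:** all patients given at least one dose of eribulin, whether or not they have a week 12 MRI.
- **Window:** events that start or worsen from first dose to 30 days after the last dose, or death if earlier.
- **Reporting:** all-cause and treatment-related rates shown separately, using the attribution already recorded under 8.3.

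Then change the start in 11.1.1 to match 11.2.1, and exempt toxicity from the Evaluability paragraph of 13.0. Recording from consent under 8.3 may stay, with pre-dose events listed but not counted in the rate. Reconcile the long-term adverse-event assessments in 10.1.1 and 10.2 with 3.5, without removing follow-up of ongoing events.

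The cost is wording. The downside is that events starting after 30 days are reported outside the rate.

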### **Evaluability**

To be evaluable for inclusion in the primary objective and secondary objectives, patients must have baseline and week 12 MRI.

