#### **Secondary Objective 2.2.1:** Objective RR

We will calculate the proportion (and 95% CI) of the patients with complete and partial response and duration of CNS response.

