#### **Secondary Objective 2.2.4:** Systemic Disease RR

For this objective, we will estimate systemic disease response rate (and 95% CI) and perform a Kaplan-Meier analysis for systemic response in this patient population

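### Treated patients who are never re-scanned drop out of the CNS and systemic response denominators, which biases both response rates upward

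*Combined protocol and SAP*

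**What the plan says.** Three rules decide who counts towards the response rates, and they differ.

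- **CNS response (Section 11.1.1).** Patients need measurable disease at baseline, and only those who "have received eribulin as per the protocol, and have had their disease re-evaluated will be considered evaluable for response". What counts as treatment per protocol is not defined.
- **Systemic response (Section 11.2.1).** Patients need measurable disease at baseline and must "have received at least one cycle of therapy, and have had their disease re-evaluated will be considered evaluable for response". There is no adherence condition here.
- **Statistics section (13.0, Evaluability).** "To be evaluable for inclusion in the primary objective and secondary objectives, patients must have baseline and week 12 MRI". Section 3.6 adds that patients without both scans "will be considered not evaluable for response and will be replaced".

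Sections 11.1.1 and 11.2.1 both carry a note on early progressors. In 11.1.1 it reads "Patients who exhibit objective disease progression prior to the end of cycle 1 will also be considered evaluable". The Evaluability paragraph has no such note.

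For secondary objective 2.2.1, Section 13.1 says "We will calculate the proportion (and 95% CI) of the patients with complete and partial response". It promises the same kind of estimate for systemic response under 2.2.4. Neither entry names a denominator, so the definitions above govern. Nothing in the document counts an unassessed patient as a non-responder, and no response rate among all treated patients is planned.

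**The concern.** Being re-evaluated is a post-baseline event that depends on how the patient fares. The calendar in Section 10.2 (footnotes d and e) ties brain MRI and body imaging to 12-week intervals for as long as eribulin continues. Neither the 30-day nor the long-term follow-up visit includes imaging. Section 3.4 ends treatment for progression, toxicity, intercurrent illness, withdrawal or death. A patient to whom one of these happens before week 12 has no scheduled response scan.

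Such patients are mostly those doing badly. Leaving them out makes the response rate, and its confidence interval, describe a favourable subset. In a small single-arm trial these rates are likely to be read as efficacy estimates for everyone treated. Correcting the week 12 rule for the primary endpoint alone would leave the filters in Sections 11.1.1 and 11.2.1 in force for objectives 2.2.1 and 2.2.4.

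**Working it through.** **1. The plan's own figure.** The plan gives no expected response rate and no expected share of unassessed patients. Its only interval is for the primary endpoint, 8 of 20 free of CNS progression. That reproduces as a Wald interval: 0.40 ± 1.96 × √(0.40 × 0.60 / 20) = 0.40 ± 0.215, or 18.5% to 61.5%. It does not bear on the response rates.

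**2. Who is counted under each rule** (patients treated, with measurable disease in the compartment at baseline):

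| Patient | 11.1.1 (CNS) | 11.2.1 (systemic) | Evaluability paragraph |
|---|---|---|---|
| Dies, deteriorates or stops in cycles 2-4, never re-scanned | out | out | out |
| Objective progression before the end of cycle 1 | in | in | out if no week 12 MRI |
| Stops in cycles 2-4 with progression on an unscheduled scan of that compartment, no week 12 MRI | in, if treated per protocol | in | out |
| Scanned responder with a treatment deviation | possibly out (term undefined) | in | in |

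The first row is the core of the point: no rule keeps these patients. The second and third rows show that the rules disagree.

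**3. Direction.** Let N be the treated patients with measurable disease, m those never re-evaluated, and R the responders. Section 11.1.4 requires a scan, and a confirming scan at least 4 weeks later, before CNS CR or PR is coded. In either compartment a patient never re-evaluated has no recorded response, so the m patients contribute nothing to R. Then R/(N − m) ≥ R/N, with equality only if m = 0 or R = 0.

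**4. Size.** With d = m/N, the evaluable-set rate is (R/N) × 1/(1 − d). The value of d is an assumption, taken as 10% to 40%. The illustration has 20 evaluable patients after replacement, all taken to have measurable disease, and 4 responders (also assumed). The reported rate is 4/20 = 20.0%, exact 95% CI 5.7% to 43.7%.

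| d | 1/(1 − d) | Treated N = 20/(1 − d), rounded up | 4/N | Exact 95% CI |
|---|---|---|---|---|
| 10% | 1.11 | 23 | 17.4% | 5.0-38.8% |
| 20% | 1.25 | 25 | 16.0% | 4.5-36.1% |
| 30% | 1.43 | 29 | 13.8% | 3.9-31.7% |
| 40% | 1.67 | 34 | 11.8% | 3.3-27.5% |

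With 6 responders, 30.0% becomes 26.1%, 24.0%, 20.7% and 17.6%.

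**5. Is the range plausible?** Section 1.4 quotes a median survival of 4 to 7.5 months by subtype. Under exponential survival (an assumption), deaths by 12 weeks (2.76 months) are 1 − 2^(−2.76/4) = 38% and 1 − 2^(−2.76/7.5) = 22.5%. This is only a guide. Some of these patients would have progression documented on a scan before death, and criterion 4.1.6 screens out disease thought likely to limit life expectancy to under 3 months. Both lower d. Stopping for toxicity or withdrawal without a scan raises it.

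**The case against.** The strongest reply is that stopping treatment is not the same as going unscanned. Section 11.1.1 asks only that disease was re-evaluated, so a patient whose unscheduled scan shows progression stays in. Section 3.4 asks that assessments be completed at discontinuation. Section 11.1.4 schedules MRI until progression, and its best-response table asks that progression be documented even after treatment stops. This stands in part. It reduces the number lost under 11.1.1 and 11.2.1, but it does not help a patient who dies or deteriorates without a scan, and the Evaluability paragraph still drops anyone without a week 12 MRI.

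Four stronger readings are tempting, and the documents do not support them.

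- *That the adherence condition affects both rates.* It appears only in the CNS definition.
- *That excluding deviators inflates the CNS rate.* A responder with a deviation would be dropped as well, so the direction is unknown. Dose delays and reductions that follow Section 7.2 are plausibly treatment per protocol.
- *That everyone who stops in cycles 2-4 disappears.* As above, those with an unscheduled scan remain under 11.1.1 and 11.2.1.
- *That the inflation can be calculated from the 3.9-month median treatment duration in Section 1.3.* With exponential stopping, 61.2% remain on treatment at 12 weeks. That gives 20/0.612, or 33 treated, and 4/20 = 20% against 4/33 = 12%. But the median comes from a different trial, the step treats every stop as a missing scan, and the 20 is the week 12 MRI set rather than the set in 11.1.1.

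Two further points are fair. Some scans are missed for reasons unrelated to outcome, such as the MRI intolerance described in Section 8.2.1. Calling those patients non-responders is a convention. Also, objectives 2.2.1 and 2.2.4 are estimation only, and the 8-of-20 success rule does not depend on them.

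**Conclusion.** The concern holds for patients who are treated, have measurable disease and are never re-evaluated. They leave both response denominators although they cannot be recorded responders, so exclusion on this ground can only raise the rates or leave them unchanged. The Evaluability paragraph adds a week 12 MRI requirement to the secondary objectives and contradicts the cycle 1 exception in Sections 11.1.1 and 11.2.1. In the CNS set only, the undefined adherence condition lets post-treatment judgement choose the denominator, with a bias of unknown direction.

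The documents do not fix the size. The factor of 1.11 to 1.67 rests on an assumed 10% to 40% never re-evaluated. The point deserves correction because the rates would be reported as efficacy estimates. A reader might infer that it undermines the trial's success criterion, but that criterion uses the 3-month CNS PFS proportion, not response.

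**What to change.** For objectives 2.2.1 and 2.2.4, state in Section 13.1 that the denominator is all patients who received at least one dose of eribulin and had measurable disease in that compartment at baseline. Count patients without a follow-up assessment as non-responders. Delete the treatment-per-protocol condition from 11.1.1. Report the evaluable-set rate as supplementary, with the number excluded and the reasons.

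Amend 11.1.1, 11.2.1, 13.1, 3.6 and the Evaluability paragraph together. If only the definitions in Section 11 change, the Evaluability paragraph would still require a week 12 MRI for both rates. If replacement under 3.6 is kept, replaced patients who received eribulin must stay in the response denominators.

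The cost is wording only; no new data are needed. The reported rates become less favourable, and scans missed for unrelated reasons will count as non-response, which is a conservative convention that the supplementary rate makes visible.
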